5.2 Secondary Efficacy Endpoints

The secondary endpoint is duration of benefit, assessed by median time to baseline VHI-10 after treatment with DAXI and via phone call surveys. VHI-10 questionnaires will be given at baseline, day 14, then monthly until loss of benefit. Phone calls will be conducted at day 5, day 14, then monthly until loss of benefit.

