9.5 Visit 4 (Phone call, Day 14*)

1. Phone call to assess clinical improvement
2. Ensure there is absence of dysphagia (using EAT-10 questionnaire), no injection site issue, or other adverse event

*Day 14 after most recent DAXI injection

9.6 Visits 5-10 (Remote Survey, every month starting 1 month after most recent injection)

1. Phone call to assess duration of benefit
2. Patient fills out PROMs electronically through Qualtrics to assess our primary (VHI-10) and secondary outcome measures

- VHI-10
 - CPIB-10
 - OMNI-VES
 - EAT-10
3. Patient records their voice in Phonalyze for CPP and CAPE-V analysis
 4. Patient will record whether DAXI still has desired effect

Data is collected monthly until loss of benefit.

For every instance when all PROMs and Phonalyze recordings are completed, patients will be paid \$10, up to \$150. After the completion of the study the number of entries will be tabulated and patient will be given a Visa gift card in the allotted amount. Patients who withdraw from the study will still be compensated for all instances when PROMs and Phonalyze recordings were completed.

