14.3 Analysis of Primary Endpoint

Our primary outcome is the difference in VHI-10 score at 8 weeks after injection with DAXI. This will be determined using a paired t-test with subjects pre-treatment VHI-10 scores as a control. Our second primary outcome measure is the duration of effect of DAXI, assessed qualitatively through phone calls, compared to patients' prior Botox treatment. We will produce a Kaplan-Meier curve to illustrate the duration of clinical benefit after treatment with DAXI.

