APPENDIX 3. FINANCIAL CONSIDERATIONS

Participants will be compensated for participation in the study. For every completed survey and VoiceEvalu8 entry, they will be paid \$10, up to \$150. At the completion of the study, the number of entries will be tabulated and the patient will be given a Visa gift card in the allotted amount.

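### Payment rises by $10 for each further month of self-reported DAXI benefit, because the paid surveys stop at loss of benefit: a small one-sided incentive that is cheap to remove

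*Combined protocol and SAP*

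**What the plan says.** Section 9.6 (Visits 5-10) contains three rules that interact:

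- Payment: "For every instance when all PROMs and Phonalyze recordings are completed, patients will be paid \$10, up to \$150". The money is given as a gift card after the study is completed.
- Stopping: "Data is collected monthly until loss of benefit". Section 5.2 says the same of the main instrument ("VHI-10 questionnaires will be given at baseline, day 14, then monthly until loss of benefit"), and the Visit 5-10 column of Appendix 1 repeats the rule.
- Source of the information: "Patient will record whether DAXI still has desired effect", alongside a phone call and the questionnaires.

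Section 5.2 makes duration of benefit the secondary endpoint, by median time to baseline VHI-10 and by phone surveys. Section 14.3 raises its standing: "Our second primary outcome measure is the duration of effect of DAXI, assessed qualitatively through phone calls". Sections 14.3 and 14.4 compare it with each subject's prior Botox treatment, which section 9.1 records as history. Section 7.2 confirms that there is no blinding.

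Appendix 3 restates the payment in other words: "For every completed survey and VoiceEvalu8 entry, they will be paid \$10, up to \$150". It is the only place that names VoiceEvalu8. Sections 5.4, 9.1 and 9.6 and Appendix 1 name Phonalyze.

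**The concern.** A subject who reports continued benefit is invited to another paid survey, and a subject who reports its loss is not. No section pays for contacts after loss of benefit, and none gives an objective or blinded criterion for that loss. The payment is therefore linked to the quantity being estimated.

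The link matters because it works on one side only. DAXI duration is collected prospectively, open label and with payment. The Botox duration it is set against comes from past treatment, with no payment stated. With no concurrent control, any tendency to report loss a survey late would be read as longer DAXI benefit.

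The same stopping rule also touches the 8-week VHI-10. Under section 5.2, a subject who reports loss at Month 1 gives no later questionnaire and could be missing from the paired test in section 14.3. Section 5.1 describes the monthly VHI-10 without the stopping clause, so the sections differ on this.

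**Working it through.** **1. The plan's own figure.** Section 14.6 gives an SD of duration of 7.2 weeks, a within-subject correlation of 0.875, N = 20, 80% power and a detectable difference of 2.4 weeks. I assume a paired t-test at two-sided alpha 0.05 (section 14.6 states 0.05 for the VHI-10 calculation).

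- SD of the difference = 7.2 × √(2 × (1 − 0.875)) = 7.2 × 0.5 = 3.6 weeks.
- With the noncentral t, 2.4 weeks gives power 80.7%, and the detectable difference at 80% power is 2.38 weeks.

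The 2.4 weeks reproduces.

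**2. Payment against reported duration.** Full sets fall at screening (section 9.1), Day 14 (Appendix 1) and six monthly contacts (Visits 5-10). I count the screening and Day 14 sets as payable. I also count the contact at which loss is reported, because section 9.6 has the subject complete the questionnaires and recording at that same contact.

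| Monthly sets completed | Monthly pay | Total with screening and Day 14 |
|---|---|---|
| 1 | $10 | $30 |
| 2 | $20 | $40 |
| 3 | $30 | $50 |
| 4 | $40 | $60 |
| 5 | $50 | $70 |
| 6 | $60 | $80 |

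A subject who stops before any monthly set would receive $20. The slope is $10 per month whichever sets are counted.

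**3. The cap.** $150 / $10 = 15 sets, against 8 scheduled. If monthly surveys ran through the full 36 weeks of participation, 36 / 4.35 = 8.3, so 8 monthly sets and 10 in all, or $100. The cap does not break the link on either count.

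**4. Scale.** One month = 365.25 / 12 / 7 = 4.35 weeks, and 4.35 / 2.4 = 1.8. A mean shift of 2.4 weeks would need 2.4 / 4.35 = 55% of subjects to report one survey late.

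**5. What-if range, not an estimate.** The documents give no share of subjects who might report late. Suppose a share f does so by one survey and there is no true difference. The mean then shifts by f × 4.35 weeks, and the SD of the difference becomes √(3.6² + f(1 − f) × 4.35²).

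| Assumed f | Mean shift (weeks) | SD (weeks) | Chance of p < 0.05 (nominal 5%) |
|---|---|---|---|
| 10% | 0.43 | 3.83 | 8% |
| 25% | 1.09 | 4.06 | 21% |
| 50% | 2.17 | 4.21 | 59% |

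The table shows only that a monthly grid is coarse relative to the target. It says nothing about whether $10 would cause any delay.

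**The case against.** The step is $10 for four questionnaires and a voice recording, paid only after study completion, and the surveys are themselves work. Payment per completed contact is a common retention device. All of this stands, and it is why the point is minor.

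There is an opposing pull. Other Botox is prohibited (section 6.2), a further laryngeal Botox injection leads to withdrawal (section 13), and a subject whose voice has worsened wants re-treatment. The net direction of reporting is therefore not established. But the wish for re-treatment was present in the prior Botox periods too, so it does not cancel an incentive found only under DAXI.

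The trigger is partly inferred. Loss of benefit is not defined, no section says literally that surveys end on the subject's own declaration, and staff also ask by phone. Sections 5.2 and 14.4 define duration by return to baseline VHI-10, and payment does not depend directly on that score. This stands as a caveat. Every route named nevertheless rests on what the subject reports.

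The planned summary is a median from a Kaplan-Meier curve, whereas the 2.4 weeks is a difference in means. A median on a monthly grid often does not move when a few subjects report late, and moves by a whole month when it does. The comparison with 2.4 weeks is for scale only.

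A reader might also infer from "For every completed survey and VoiceEvalu8 entry, they will be paid" that Appendix 3 pays per item. Five items at three contacts would reach $150 at Month 1, leaving nothing for the 8-week contact. That reading is strained: the amount, cap and tabulated entries match section 9.6, and Appendix 3 reads naturally as a shorter statement of the same rule. It would also remove the later link to duration. What stands is that the two wordings and the two app names need to be made the same.

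**Conclusion.** The incentive is real on the text: $10 for each further month of reported benefit, at most $60 over Visits 5-10, uncapped in practice and present only on the DAXI side of an open-label, uncontrolled comparison.

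A reader might infer that the DAXI duration is biased upward, or that the duration outcome is invalid. The documents do not support that. They contain no data on late reporting, the sum is small and deferred, and they do not show what subjects are told about payment ending. The size of any effect cannot be estimated from them, and the what-if shares above are assumptions.

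The conclusion rests on reading loss of benefit as a subject-reported event and on counting the screening and Day 14 sets as payable. The second assumption changes the totals but not the slope. This is a cheap improvement of minor severity.

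**What to change.** - **Schedule.** Keep the remote surveys at all six scheduled months (Visits 5-10) for every subject, including after reported loss of benefit. The duration endpoint would still be dated from the loss, and the 8-week VHI-10 would be kept for subjects who lose benefit early.
- **Payment.** Pay $10 per completed set at each of these contacts, whether or not benefit is reported to persist. Do not pay a sum on the report of loss, which would create the reverse incentive.
- **Where to amend.** Change the stopping wording in sections 5.2 and 9.6 and Appendix 1, and the payment wording in section 9.6 and Appendix 3. Reconcile this with the withdrawal rule in section 13, which limits contacts after loss for subjects who are re-injected.
- **Harmonise.** Use one payment unit (the complete set) and one app name in section 9.6 and Appendix 3. State what a complete set contains, since section 9.6 lists EAT-10 at Visits 5-10 and Appendix 1 does not.

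**Cost.** At most 6 × $10 = $60 per subject, or 20 × $60 = $1,200 in all. The total per subject stays at $80, within the $150 cap. There are a few more remote contacts for subjects who lose benefit early, and an IRB amendment is needed.

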9.7 Early Withdrawal Visit

N/A

10 ADVERSE EXPERIENCE REPORTING AND DOCUMENTATION

10.1 Adverse Events

An adverse event (AE) is any untoward medical occurrence in a clinical investigation of a patient administered a pharmaceutical product and that does not necessarily have a causal relationship with the treatment. An AE is therefore any unfavorable and unintended sign (including an abnormal laboratory finding), symptom or disease temporally associated with the administration of drug product, whether or not related to that product. An unexpected AE is one of a type not identified in nature, severity, or frequency in the current Package Insert or of greater severity or frequency than expected based on the information in the Package Insert.

The Investigator will probe, via discussion with the subject, for the occurrence of AEs during each subject visit and record the information in the site's source documents. Adverse events will be recorded in the patient CRF. Adverse events

will be described by duration (start and stop dates and times), severity, outcome, treatment and relation to study drug, or if unrelated, the cause.

10.1.1 AE Severity

The National Cancer Institute's Common Terminology Criteria for Adverse Events (CTCAE) Version 3.0 should be used to assess and grade AE severity, including laboratory abnormalities judged to be clinically significant. The modified criteria can be found in the study manual. If the experience is not covered in the modified criteria, the guidelines shown in Table 1 below should be used to grade severity. It should be pointed out that the term "severe" is a measure of intensity and that a severe AE is not necessarily serious.

Table 1. AE Severity Grading

Severity (Toxicity Grade)	Description
Mild (1)	Transient or mild discomfort; no limitation in activity; no medical intervention or therapy required. The subject may be aware of the sign or symptom but tolerates it reasonably well.
Moderate (2)	Mild to moderate limitation in activity, no or minimal medical intervention/therapy required.
Severe (3)	Marked limitation in activity, medical intervention/therapy required, hospitalizations possible.
Life- threatening (4)	The subject is at risk of death due to the adverse experience as it occurred. This does not refer to an experience that hypothetically might have caused death if it were more severe.

10.1.2 AE Relationship to Study Drug

The relationship of an AE to the study drug should be assessed using the following the guidelines in Table 2.

Table 2. AE Relationship to Study Drug

Relation ship to Drug	Comment
Definitely	Previously known toxicity of agent; or an event that follows a reasonable temporal sequence from administration of the drug; that follows a known or expected response pattern to the suspected drug; that is confirmed by stopping or reducing the dosage of the drug; and that is not explained by any other reasonable hypothesis.
Probably	An event that follows a reasonable temporal sequence from administration of the drug; that follows a known or expected response pattern to the suspected drug; that is confirmed by stopping or reducing the dosage of the drug; and that is unlikely to be explained by the known characteristics of the subject's clinical state or by other interventions.
Possibly	An event that follows a reasonable temporal sequence from administration of the drug; that follows a known or expected response pattern to that suspected drug; but that could readily have been produced by a number of other factors.
Unrelated	An event that can be determined with certainty to have no relationship to the study drug.

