1.2 Overview of Clinical Studies

Injectable daxibotulinumtoxinA (DAXI, Revance Therapeutics Inc., Newark, CA) has received FDA approval for treatment of glabellar lines and has been shown in large clinical trials to provide safe, effective treatment for cervical dystonia. DAXI may offer a longer-lasting result when compared with onabotulinumtoxin.

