4 STUDY DESIGN

4.1 Study Overview

This is a single-center, open-label, dose-escalation trial. 20 subjects are planned. Each subject will be administered a single dose of DAXI. If the subject does not achieve the desired self-reported voice improvement, at 1 week post injection an additional dose of DAXI will be administered.

Screening data will be reviewed to determine subject eligibility. Subjects who meet all inclusion criteria and none of the exclusion criteria will be entered into the study.

The following treatment regimens will be used:

- Injection of DAXI at the following doses: 0.625, 1.25, 2.5 units depending on subject's current standard dose of Botox.

Total duration of subject participation will be 36 weeks. Total duration of recruitment and completion of all procedures of the study is expected to be up to 2 years.

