7.3 Formulation of Test and Control Products

7.3.1 Formulation of Test Product

Injectable daxibotulinumtoxinA (DAXI, Revance Therapeutics Inc., Newark, CA) is a FDA-approved botulinum toxin type A indicated for the treatment of glabellar lines. It has been shown in large clinical trials to provide safe, effective treatment for cervical dystonia and may offer longer-lasting results when compared with onabotulinumtoxinA. DAXI will be reconstituted using sterile saline into 1mL syringes at the desired dosage similar to clinical care for Botox.

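### The AE causality scale (Section 10.1.2, Table 2) has no grade for a well-timed AE that fits no known or expected DAXI pattern, and two of its other conditions do not work as worded

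*Combined protocol and SAP*

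**What the plan says.** Sections 8.1.9 and 10.1 require the relation to study drug to be recorded for every AE. Section 10.1 adds that the cause is recorded if the event is unrelated. Section 10.1.2 refers the assessor to Table 2, which has four grades:

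- *Definitely* opens with "Previously known toxicity of agent; or an event that follows a reasonable temporal sequence from administration of the drug". The second alternative goes on to require a known or expected pattern, confirmation on stopping or reducing, and no other reasonable explanation.
- *Probably* requires reasonable timing and an event "that follows a known or expected response pattern to the suspected drug; that is confirmed by stopping or reducing the dosage of the drug", with other explanations unlikely.
- *Possibly* requires reasonable timing and an event "that follows a known or expected response pattern to that suspected drug; but that could readily have been produced by a number of other factors".
- The last grade, *Unrelated*, is "An event that can be determined with certainty to have no relationship to the study drug".

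There is no grade for unlikely, unknown or not assessable.

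Three other places bear on this. Section 10.1 foresees events outside the known list: "An unexpected AE is one of a type not identified in nature, severity, or frequency in the current Package Insert". Section 7.3.1 describes DAXI as an "FDA-approved botulinum toxin type A indicated for the treatment of glabellar lines", and Section 1.2 adds trial experience in cervical dystonia, so laryngeal injection is a new setting for the product as the documents describe it. Section 4.1 states: "Each subject will be administered a single dose of DAXI", with one additional dose if the desired voice improvement is not reached.

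**The concern.** A causality scale should give each AE one grade. This one ties every grade of relatedness to prior knowledge of the reaction and ties *Unrelated* to certainty, which leaves a space between them. The events that fall there are unforeseen ones with plausible timing, and a trial at a new injection site should be able to record those cleanly. Section 13 itself lists unexpected voice, swallowing and breathing problems among the items for regular review.

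The *Definitely* row has the opposite weakness. Its opening alternative attaches no timing or alternative-cause condition to a known toxicity, while participation lasts up to 36 weeks. The trial has no control group, so the investigator's attribution is the only means the documents state for separating drug effects from background events. If the definitions cannot be applied as written, assessors must improvise, and the recorded attributions will not have a common meaning.

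**Working it through.** The plan states no figure on this point. The check is to write Table 2 as rules and see which events each rule admits.

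**Conditions set by each row**

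| Grade | Reasonable timing | Known or expected pattern | Confirmed on stopping or reducing | Other explanation |
|---|---|---|---|---|
| *Definitely*, first alternative | not asked | known toxicity | not asked | not asked |
| *Definitely*, second alternative | required | required | required | none reasonable |
| *Probably* | required | required | required | unlikely |
| *Possibly* | required | required | not asked | readily available |
| *Unrelated* | certainty of no relationship | | | |

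**Profiles.** Take events that are not certainly unrelated. Prior knowledge has 3 states: no known or expected pattern, known or expected pattern only, known toxicity. Timing has 2, confirmation has 2, and other explanation has 3 (none, unlikely, readily available). That gives 3 × 2 × 2 × 3 = 36 profiles. These are logical combinations and say nothing about how often each would occur.

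**Two readings of *Definitely*.** Reading 1 (literal): known toxicity alone suffices. Reading 2: known toxicity replaces only the timing condition, and the rest of the row still applies.

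**Step 1, the gap.** With reasonable timing and no known or expected pattern there are 2 × 3 = 6 profiles. Every related row fails on the pattern condition and *Unrelated* fails on certainty. Under both readings, 0 of 6 receive a grade.

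**Step 2, known toxicity without reasonable timing.** Again 6 profiles. Under reading 1 all 6 are *Definitely*, including those readily explained by something else. Under reading 2, 1 of 6 is *Definitely* (confirmed, no other explanation) and the other 5 have no grade. Neither reading requires timing. Reading 1 also creates an overlap: a well-timed known toxicity that is unconfirmed and readily explained otherwise meets both *Definitely* and *Possibly*.

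**Step 3, confirmation on stopping or reducing.** After one injection with one optional repeat there is normally no continuing dose to stop or reduce. Setting this condition to unmet leaves 3 × 2 × 3 = 18 profiles. *Probably* and the second alternative of *Definitely* cannot then be reached. A well-timed event with an expected pattern that is not a known toxicity is gradable only if other factors readily explain it. If other explanations are unlikely or absent, so that the case for the drug is stronger, it has no grade.

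**Totals without a grade**

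| | Reading 1 | Reading 2 |
|---|---|---|
| All profiles | 20 of 36 | 27 of 36 |
| Confirmation unmet | 11 of 18 | 16 of 18 |

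**Step 4, where the field is used.** The synopsis summarises toxicities by type, severity, onset, duration and outcome, and does not name relatedness. The safety set in Section 14.1 does not use causality. SAEs are documented and reported whatever their cause (Sections 10.2.1 and 16.2). In Section 13, neither the AE review nor the halting criteria refer to relatedness.

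**The case against.** The strongest case on the other side has four parts.

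1. *The consequence is small.* A reader might infer that the safety conclusion rests on relatedness tables and that these would be wrong. The documents do not support that: no such table is planned, and an unforeseen event would still be captured, graded for severity, reviewed and, if serious, reported. This stands and sets the limit of the point.

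2. *New harms would not be filed as Unrelated.* A reader might infer that novel laryngeal events are pushed into that grade. On the wording they are barred from it, because it needs certainty and Section 10.1 then asks for the cause. They are unclassifiable. Which grade an assessor would choose cannot be known, so no direction of bias follows. This also stands.

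3. *Known or expected is wider than already observed with DAXI.* An assessor could call an event expected from the pharmacology or from earlier laryngeal BotoxA treatment, which every subject has had (Section 5.6). Section 2.1 already names swallowing and breathing difficulty, and Appendix 4 lists trouble speaking or swallowing, breathing problems, cough and hoarseness. This narrows the gap to truly unforeseen events. It does not close it, and Table 2 gives no guidance on what counts as expected.

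4. *The literal reading of Definitely is uncharitable.* It would leave the middle grades almost empty, and Section 10.1.2 calls the table guidelines. So it should not be claimed that every known toxicity will be graded *Definitely*: reading 2 gives that for only 1 of 6 mistimed profiles. Timing is still missing under reading 2, and a definition that needs a charitable reading will be read differently by different assessors. Which events count as known toxicities depends on the Package Insert, which the documents do not reproduce.

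**Conclusion.** The point holds as a defect in a recording definition. Table 2 is not exhaustive: a well-timed AE with no known or expected pattern, and no certainty of being unrelated, has no grade under either reading, although a relation is mandatory. On its literal wording, *Definitely* admits a known toxicity regardless of timing or other causes. Confirmation by stopping or reducing can hardly be met in this design, so *Probably* is close to unusable.

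The reach is limited to the relatedness field on the CRF and any AE description built on it. The number of events affected cannot be derived from the documents; the profile counts show where the definitions fail and are not expected frequencies. The conclusion rests on taking the wording of Table 2 as the operative rule and on the safety summary staying as the synopsis describes it. Section 14 foresees a separate detailed SAP. If that adds tables by relatedness, the defect would carry into them.

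**What to change.** Reword Table 2 and the matching CRF help text so that every AE meets exactly one grade:

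- *Definitely*: delete the free-standing known-toxicity alternative, so that timing and the absence of another reasonable explanation are always required.
- *Definitely* and *Probably*: apply the stopping-or-reducing criterion only where applicable. This must accompany the deletion; otherwise *Definitely* loses its only practical route and nearly all related events fall to *Possibly*.
- *Possibly*: any event that does not meet *Definitely* or *Probably* and for which a drug cause cannot be excluded, whether or not the pattern is already known.
- *Unrelated*: only events for which a drug cause is excluded, because the timing is incompatible with the drug or because another cause is established and recorded as Section 10.1 requires. A looser test, such as another cause being more likely, would overlap with *Possibly* and make unforeseen events easier to dismiss.
- State that the highest grade met applies, which settles the boundary between *Definitely* and *Probably*.

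The cost is the rewording of one table and the help text, with somewhat more events graded *Possibly*. Visits, sample size and treatment are unaffected.
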